9.4.3 ANALYSIS OF THE SECONDARY ENDPOINTS

This study has four secondary endpoints.

- The incidence, severity and relationship to MMV367 of adverse events as determined by self-reported symptoms, clinical laboratory analysis, vital signs, physical examinations and ECG assessments.

- The incidence, severity and relationship to the malaria challenge agent of adverse events as determined by self-reported symptoms, clinical laboratory analysis, vital signs, physical examinations and ECG assessments. Additionally, the severity of the induced malaria infection in each participant graded by the malaria clinical score.
- The pharmacokinetics of MMV367 calculated using non-compartmental methods (C_{\max} , t_{\max} , AUC_{last} , AUC_{inf} , CL/F , Vz/F , λ , $t_{1/2}$).
- The parasite clearance kinetics following dosing with MMV367 (PRR_{48} and $PCt_{1/2}$).

Safety parameters:

The safety and tolerability of MMV367 and the malaria challenge agent will be assessed by clinical review of the following parameters:

- AEs (including SAEs and AESIs)
- Vital signs
- 12-lead ECGs
- Clinical laboratory analysis
- Physical examination

In addition, the malaria clinical score will be used to assess the severity of the induced malaria infection (see Section 8.2.4).

The analysis of this endpoint is discussed in Section 9.4.4 below.

Parasite clearance kinetics:

The parasite clearance kinetics following dosing with of MMV367 will be determined by calculating the parasite reduction ratio over a 48 hour period (PRR_{48}) and corresponding parasite clearance half-life ($PCt_{1/2}$).

The PRR_{48} will be estimated using the slope of the optimal fit of the log-linear relationship of the parasitaemia decay. The optimal fit will be derived using summarised replicate parasitaemia data, which have been cleaned by dealing with potential outliers, values below the limit of detection and non-detectable values. The optimal fit of the log-linear parasitaemia-by-time relationship is determined by using left and right censoring to systematically remove the potential lag phase and tail phase of the parasitaemia decay. The decay rate, estimated by the slope coefficient from the log-linear decay regression, will be calculated for each participant. The overall dose-specific PRR_{48} will be estimated with its 95% CI by calculating the weighted average slope estimate and corresponding standard error (SE) using an inverse-variance method. Only participants who have optimal regression models with appropriate fit contribute toward the dose-specific PRR_{48} . Details will be presented in the SAP.

The parasite clearance half-life ($PCt_{1/2}$) will be derived from the optimal decay rate. $PCt_{1/2}$ is a transformation of PRR_{48} into a per hour clearance rate. Details regarding the calculation of this parameter will be presented in the SAP.

PK parameters:

The following PK parameters will be determined using non-compartmental methods from plasma MMV367 concentration-time profiles: AUC_{last} , AUC_{inf} , C_{max} , t_{max} , $t_{1/2}$, CL/F , Vd/F and λ . When applicable, all PK variables (normally and log-normally distributed) will be summarized using arithmetic and geometric means, minimum, median, maximum, standard deviation (SD) and coefficient of variation (CV %) of arithmetic and geometric means. Summary tables showing the median and range for t_{max} and geometric mean and CV% for all other PK variables will be provided by dose.

Plasma concentration values below the lower limit of quantification will be set to zero. All mentioned parameters will be expressed as mean \pm SD, unless otherwise stated. Details regarding the calculation of this parameter will be presented in the SAP.

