12.1.5 INPATIENT OBSERVATION AND IMP ADMINISTRATION (DAY 7PM TO DAY 11)

Participants will be admitted to the clinical trial unit on Day 7PM, in preparation for single-dose administration of MMV367 on Day 8 when parasitaemia for the majority of participants is expected to be above 5,000 parasites/mL. Participants will be provided with a light snack the evening prior to dosing and then fast from all food and drink (except water) for a minimum of 8 h on the day prior to dosing until approximately 4 h post-dose, at which time lunch will be provided.

The following procedures will occur on admission to the clinical trial unit Day 7PM:

- Alcohol breath test.
- Urine drug screen.
- Urine β -hCG pregnancy test for WOCBP.
- Perform COVID-19 rapid test.

The following procedures will occur pre MMV367 administration on Day 8:

- Perform abbreviated physical examination.
- Obtain and review a 12-lead ECG.
- Obtain malaria clinical score.
- Record vital signs.
- Record AEs and use of concomitant medications.
- Review haematology and biochemistry results from Day 7 am collection.
- Randomisation.
- Cannulate participants with an indwelling intravenous (18 or 20 gauge) cannula.
- Collect blood samples for
 - haematology and biochemistry,
 - malaria PCR,
 - parasite *ex vivo* viability,
 - IMP PK (baseline sample),
 - future malaria research sample (if participant consented).

Administer the relevant MMV367 dose under direct observation.

The following procedures will occur after MMV367 administration:

- Follow up participants as in-patients until Day 11 to ensure tolerance of MMV367 and adequate clinical response.
- Perform symptom-directed physical examination if clinically indicated.
- Record vital signs three times a day (at time points specified in Section 1.3) whilst confined.
- Obtain malaria clinical score three times a day (at time points specified in Section 1.3) whilst confined.
- Obtain 12-lead ECG once daily (at time points specified in Section 1.3) while confined.
- Collect blood for haematology and biochemistry at 24 hours post-MMV367 administration.
- Collect blood for malaria PCR following MMV367 administration at 2, 4, 8, 12, 16, 24, 30, 36, 48, 54 and 60 hours (see section 8.1 and 8.2 for time allowed time windows).
- Collect blood samples for IMP PK at 1, 2, 3, 4, 6, 8, 12, 16, 24, 36, 48 and 60 hours post-MMV367 administration (see section 8.1 and 8.2 for time allowed time windows).

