##### Handling of missing data

Missing parasitaemia data will not be imputed. For any replicates that were non-detects (ND), the value will be substituted with 1 parasite/mL prior to calculating the geometric mean for parasitemia quantified from qPCR.

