#### 11.1.2 Parasite clearance kinetics

The Parasite Reduction Ratio (PRR) and corresponding parasite clearance half-life ( $PCt_{1/2}$ ) of asexual parasites is derived from the clearance rate of parasitaemia after administration of MMV367 treatment. The analysis of PD response to investigational antimalarial therapy consists of:

- calculating the optimal parasite clearance rate (slope coefficient from the log-linear decay regression of qPCR data) for each individual, then,
- estimating dose specific parasite clearance rate and 95% confidence interval (CI) by calculating the weighted average slope estimate and corresponding standard error (SE) using an inverse-variance method.

The data used for all model selection and fitting calculations is comprised of the  $\log_{10}$  transformed geometric mean of parasitaemia per time point per participant up to the first time point all parasitaemia replicates are ND. If during initial parasite clearance there are no samples ND for a participant, the last time point included in the analyses will be three time points after the minimum observed parasitemia value. All subsequent time points are set to 'missing' regardless of whether parasitaemia values increased afterwards due to potential

recrudescence. Sensitivity analyses may be performed using other thresholds to determine parasite clearance, for example, but not limited to, the lower limit of quantification (LOQ) (i.e. the lower limit of the reportable range) of 32 parasites/mL or limit of detection of 111 parasites/mL [1], to assess robustness of PRR estimates.

The PRR per 48 hours,  $PRR_{48}$ , for asexual parasite will be estimated using the slope of the optimal fit of the log-linear relationship of the parasitaemia decay over time from MMV367 administration for each individual, as detailed in CTM QIMR SOP 41 and Marquart et al. [2]

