#### Regression Modelling to Determine Optimal Fit

A regression modelling approach to remove potential lag and/or tail phases of the parasitaemia decay profile will be used to determine the optimal log-linear decay regression. The algorithm considers removing parasitaemia data points in an iterative process from both ends of the parasitaemia curve, i.e. a combination of right censoring (removing values from the tail phase) and left censoring (removing values from the lag phase), and uses model selection techniques to find the optimal log-linear regression.

The algorithm to obtain the log-linear decay for each participant is based on the log-linear regression detailed in Equation (1), where Time is the number of hours since administration of antimalarial treatment ( $Time = 1, \dots, m$ ), and  $\beta_0$  and  $\beta_1$  are the intercept and slope estimates, respectively.

$$\log_{10} Parasitemia = \beta_0 + \beta_1 Time \quad (1)$$

Based on the parasitaemia data for each participant, the iterative algorithm to determine the optimal log-linear decay for each participant is summarised in Table 2. The iterative algorithm is continued until a minimum of four observations are available.

The optimal log-linear regression model for a participant is deemed an appropriate fit if the overall model p-value  $< 0.001$ .

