### Estimating Dose Specific PRR (PRR48,D)

Of the participants with appropriate overall fit ( $p < 0.001$ ), the average  $PRR_{48}$  and corresponding 95% CI for each cohort is estimated by using the inverse variance method to calculate the weighted average linear regression slope ( $\bar{\beta}_1$ ) and corresponding SE. The weighted average slope for  $s$  participants in the dose with appropriate overall fit is given by Equation (4):

$$\bar{\beta}_1 = \frac{\sum_{i=1}^s (w_i \times \beta_{1,i})}{\sum_{i=1}^s w_i}, \quad i = 1, \dots, s \quad (4)$$

where the weight is the inverse of the squared standard error,  $w_i = \frac{1}{SE(\beta_{1,i})^2}$ . The standard error of  $\bar{\beta}_1$  is estimated as,  $SE(\bar{\beta}_1) = \sqrt{\frac{1}{\sum_{i=1}^s w_i}}$ .

Therefore the dose specific PRR (PRR48,D) and corresponding 95% confidence interval is estimated as shown in Equation (5) and (6), respectively:

$$PRR_{48,D} = 10^{-48 \times \bar{\beta}_1} \quad (5)$$

$$95\% \text{ CI: } 10^{-48 \times (\bar{\beta}_1 \pm 1.96 \times SE(\bar{\beta}_1))} \quad (6)$$

PRR48 estimates will also be reported as  $\log_{10}(PRR_{48})$ .

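### Inverse-variance weights tend to favour slow clearers, so the dose-specific PRR48 falls below the equal-weight mean of the same participants' slopes whenever response varies

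*Protocol*

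**What the plan says.** Protocol 9.4.3 pools the individual decay slopes within a dose by "calculating the weighted average slope estimate and corresponding standard error (SE) using an inverse-variance method". SAP 11.1.2 repeats this ("using the inverse variance method to calculate the weighted average linear regression slope") and defines w_i: "where the weight is the inverse of the squared standard error". The pooled SE is √(1/Σw_i). Neither formula has a term for variation between participants.

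The data entering each regression run "up to the first time point all parasitaemia replicates are ND". If no sample is ND, "the last time point included in the analyses will be three time points after the minimum observed parasitemia value". For an ND replicate, "the value will be substituted with 1 parasite/mL prior to calculating the geometric mean". SAP Table 2 then trims points from either end, down to four at the least, and keeps the window with the smallest p-value. A participant contributes to the dose estimate only if p < 0.001.

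The same weights enter the between-dose test (SAP Equations 9 and 10). The only sensitivity analyses mentioned for PRR48 vary the threshold that defines clearance. No unweighted or random-effects estimate is planned.

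**The concern.** Inverse-variance weighting suits several estimates of one common quantity whose precision is unrelated to their value. Neither condition is assured here. Participants on one dose may clear at different rates, and the precision of a slope depends on how long the decay is observed, which depends on the slope itself. The weight is then partly a function of the outcome being averaged.

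PRR48 and its half-life PCt1/2 form a secondary endpoint, reported by dose and compared across doses. A reader will take the dose figure as the average response of that dose's participants. If slow clearers carry most of the weight, it is not that average. Widening the confidence interval alone would leave the point estimate where it is.

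**Working it through.** The documents give no pooled PRR48 to reproduce, so the check starts from the weights.

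**1. Formula.** For a straight-line fit, SE(β_1,i) = s_i/√Sxx_i, where s_i is the residual SD and Sxx_i = Σ(t − t̄)² over the retained times. Hence w_i = Sxx_i/s_i². With equal scatter, the weight is proportional to Sxx, that is, to the number and spread of the retained times.

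**2. Inputs.** Protocol 12.1.5: "Collect blood for malaria PCR following MMV367 administration at 2, 4, 8, 12, 16, 24, 30, 36, 48, 54 and 60 hours". The pre-dose, 72 h and outpatient samples (96 h, 120 h and later) are in the Schedule of Activities. Assumed: baseline 10,000/mL (the protocol expects more than 5,000/mL in most participants), detection to 10/mL, equal scatter, straight-line decay.

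**3. Three participants with log10 PRR48 of 2, 3 and 4.** The line falls from 4 to 1 on the log10 scale at 48 × 3/PRR hours: 72, 48 and 36 h.

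| log10 PRR48 | Last time (h) | Points | Sxx (h²) | Weight |
|---|---|---|---|---|
| 2 | 72 | 13 | 6,956 | 65.6% |
| 3 | 48 | 10 | 2,320 | 21.9% |
| 4 | 36 | 9 | 1,320 | 12.5% |

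Pooled: 0.656×2 + 0.219×3 + 0.125×4 = 2.47, against a plain mean of 3.00. The shift of -0.53 is a factor 10^0.53 = 3.4 in PRR48. With 2.3, 2.9 and 3.5 the weights are 57/27/16%, and the pooled value is 2.65 against 2.90, a factor 10^0.25 = 1.8. Changing the floor to 1, 32 or 111/mL moves the 2/3/4 result only to 2.52, 2.42 or 2.51. Keeping the next sample as the ND point gives Sxx of 11,230, 3,498 and 2,320 and a pooled 2.48. These trios are illustrations, with SDs of 1.0 and 0.6.

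**4. Simulation of the SAP algorithm** (triplicates, ND = 1/mL, window rules, Table 2 trimming, p < 0.001 filter, Equation 4; centre 2.9, residual SD 0.25 log10, ND threshold 10/mL, early-treatment cut-offs applied). Entries are differences in mean log10 PRR48 from the equal-weight mean.

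| Assumed between-participant SD | Weighted, n=2 | Weighted, n=3 | Weighted, n=6 | Random effects, n=3 |
|---|---|---|---|---|
| 0 | -0.04 | -0.05 | -0.06 | -0.03 |
| 0.3 | -0.07 | -0.09 | -0.13 | -0.03 |
| 0.6 | -0.15 | -0.20 | -0.30 | -0.03 |
| 1.0 | -0.33 | -0.48 | -0.62 | -0.04 |
| 1.41 | -0.45 | -0.60 | -0.90 | -0.04 |

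At n = 3 and SD 0.6 to 1.41, the slowest clearer held the largest weight in 62-76% of simulated groups. A second simulation of 28 settings put the weighted mean at or below the equal-weight mean in all of them (0 to -0.6; -0.13 to -0.31 at SD 0.6).

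SD 1.41 comes from the 20 mg prediction in Protocol 4.3: (5.8 − 0.26)/3.92 = 1.41. It is an upper limit, because that interval may include parameter uncertainty.

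**5. Source of variation.** In a sigmoid-Emax version at n = 3, the shift was about -0.08 when only EC50 varied and -0.63 to -0.74 when Emax varied as well.

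**6. Against the true mean.** An ND point kept at 1/mL, below the assumed 10/mL floor, steepens individual slopes. With it kept, at SD 0.6, the weighted estimate was off by -0.06 to +0.10 and the equal-weight mean by +0.25 to +0.32. Root-mean-square errors were similar (0.40-0.51 and 0.40-0.54). With the ND point left out and a 20% CV (SD 0.58 at 2.9), the weighted estimate was off by -0.18 (n=3) to -0.23 (n=6) and the equal-weight mean by only -0.03 to -0.05.

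**The case against.** The strongest reply is that low relative to the participants' plain mean is not the same as low relative to the truth. The SAP's ND substitution only has a use if ND replicates enter the fit, so keeping the ND point is the natural reading. Step 6 shows that the equal-weight mean is then the more biased of the two at SD 0.6, and in some settings it has slightly the larger error. This stands. A reader might infer that the dose-specific PRR48 is generally biased low; the documents do not support that without the ND handling, the assay floor and the spread all being known. The upward bias is, however, a fault in the individual slopes. Two errors that happen to offset each other are no reason to keep the weighting.

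Second, the size rests on SDs and noise levels that the documents do not give. This also stands, so the result is shown as a range.

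Third, the consequence is limited. The SAP's general approach is descriptive, the primary PK/PD model derives its own PRR48 (Protocol 9.4.2), and individual PRR48 values will be listed (SAP 11.1.3), so an unweighted mean could be formed by hand. This lowers the stakes, but the headline dose figures and the between-dose test would still use the weights.

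Fourth, an equal-weight t interval is wide: the multiplier is 12.7 at n = 2 and 4.3 at n = 3. True, but that width shows how little two or three participants say about a dose mean.

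**Conclusion.** The point holds relative to the equal-weight mean of the same participants' slopes. Slow clearers tend to get the most weight, and the dose-specific log10 PRR48 is pulled down by about 0.1 to 0.3 at an assumed between-participant SD of 0.6 (a factor of 1.3 to 2.0 in PRR48) and by about 0.3 to 0.6 at SD 1.0 (2.0 to 4.0). The shift is near zero without variation, small if only EC50 varies, and absent where one participant contributes, as at 1500 mg in Cohort 1. Residual scatter also moves the weights, so the ordering is a tendency, not a rule.

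Two further readings are tempting but go too far. One is that the estimate is simply the slope of the slowest clearers; in the 2/3/4 example it is 2.47, not 2. The other is that the shift is worst at low or intermediate doses and so distorts the dose-response in a known way. The documents give no between-participant SD by dose, and the review team chooses the doses and numbers after Cohort 1.

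**What to change.** In Protocol 9.4.3 and SAP Equations 4-6, make the main dose-specific slope one of the following, chosen in advance:

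- the equal-weight mean of the participant slopes, with SE = SD/√n and a t interval; or
- a random-effects mean, with weights 1/(SE_i² + τ²), where τ² is the between-participant variance.

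Derive PRR48 and PCt1/2 from that slope. Use the same dose means and variances in the between-dose comparison (Equations 9 and 10). At a dose with one participant, show only that participant's value, and state how such a dose enters the comparison. Keep the inverse-variance estimate as a sensitivity result for comparison with earlier studies.

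In the 24 simulated settings with between-participant variation, equal-weight or random-effects pooling had lower or near-equal root-mean-square error. The SD/√n t interval covered 89-97%, against 10-47% for Equation 6.

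Separately, the SAP should say whether the first all-ND point is fitted at 1/mL, since that decides the direction of bias in the individual slopes.

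The cost is document wording and a few lines of R, with no new data. The downsides are wider intervals at n = 2-3 and a main figure computed differently from earlier studies, so both figures may need to be shown.

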9.4.4 SAFETY ANALYSES

All AE data will be listed for each participant, including severity, relationship to IMP (MMV367) and malaria challenge agent, relationship to other protocol-specific treatments, outcome and actions taken. In addition, listings of AEs leading to discontinuation, AESIs, SAEs and deaths, will be provided as applicable. Adverse events (AE) will be coded according to MedDRA and grouped by system organ class (SOC) and preferred term (PT).

Clinical laboratory parameters, physical examination results, vital signs, and 12-lead ECG results will be listed for all participants and visits. Summary tables for each scheduled visit, including observed values, change from each baseline and clinical significance of each abnormal value, will be presented.

Malaria clinical score data (total score and each sign/symptom individually) will be listed for all participants and visits.

9.4.5 BASELINE DESCRIPTIVE STATISTICS

Demographic data will be summarised by descriptive statistics and listed for all enrolled participants. This will include total number of observations, mean, standard deviation, and range for continuous variables for medians and number and percentages for categorical variables.

Participant disposition will be summarised and presented in a flow diagram. Trial completion, trial withdrawals, exclusions, and violations will be summarised and the reasons for withdrawal, exclusions, and violations will be listed.

Medical history, current medical conditions, prior and concomitant medications, results of laboratory screening tests, drug and alcohol screening tests, and any other relevant baseline information will be listed by participant and treatment group. Medical history will be coded using MedDRA and summarised by SOC and PT.

9.4.6 PLANNED INTERIM ANALYSES

This study has no formal interim analyses other than review of safety, tolerability, parasitaemia and PK data by the SDRT between cohorts.

9.4.7 SUB-GROUP ANALYSES

Not applicable.

9.4.8 TABULATION OF INDIVIDUAL PARTICIPANT DATA

All individual participant data will be listed by measure and time-point.

9.4.9 EXPLORATORY ANALYSES

No formal statistical analysis is planned for exploratory endpoints.

10 SUPPORTING DOCUMENTATION AND OPERATIONAL CONSIDERATIONS

10.1 REGULATORY, ETHICAL, AND STUDY OVERSIGHT CONSIDERATIONS

10.1.1 ETHICAL STANDARD

The trial will be conducted in accordance with the protocol approved by the HREC(s), the principles of the Declaration of Helsinki (Recommendations guiding Medical Doctors in Biomedical Research Involving Human Participants, Fortaleza, Brazil 2013), the NHMRC National Statement on Ethical Conduct in Human Research (2007, updated 2018) and the Integrated Addendum to ICH E6 (R1): Guideline for Good Clinical Practice E6 (R2) (November 2016) — with introductory comments of the Australian TGA.

The Principal Investigator will minimise any discomfort experienced by participants during the trial. The only invasive procedures will be the IV inoculation of the malaria challenge agent and the blood collection by cannulation/venepuncture. The total volume of blood drawn from each participant will not exceed 470 mL in any 30-day period during trial participation.

10.1.2 ETHICAL REVIEW

The protocol, Participant Information Sheets, and Informed Consent Forms will be reviewed by the approving HREC(s) and no trial activities will be initiated prior to approval. All amendments and addenda to the protocol and consent forms will similarly be submitted to the approving HREC(s) for approval prior to their implementation.

Changes to the final trial protocol can only be made with the prior consent of the Principal Investigator, the Sponsor and the approving HREC(s). All such changes must be attached to (or incorporated into) the

final protocol and communicated to all relevant members of the clinical trial unit staff and, if appropriate, to trial participants. All deviations from this trial protocol will be included in the trial master file and included in the CSR. The types of amendments are discussed below.

Administrative or minor changes

Administrative or minor changes include but are not limited to changes in trial staff or contact details (e.g., Sponsor instead of contract research organisation monitors). Amendments for administrative or minor changes may be suitable for executive review (expedited) by the approving HREC(s).

Substantial amendment

Significant changes require a substantial amendment. Significant changes include but are not limited to: new data affecting the safety of participants, change of the objectives/endpoints of the trial, eligibility criteria, dose regimen, trial assessments or procedures, treatment or trial duration with or without the need to modify the Participant Information Sheet and Informed Consent Form. Substantial amendments are to be approved by the HREC(s). The implementation of a substantial amendment can only occur after formal approval from the Sponsor, HREC(s), and Principal Investigator.

Urgent amendment

An urgent amendment might become necessary to preserve the safety of the participants included in the trial. The requirements for approval should in no way prevent any immediate action being taken by the Principal Investigator or the Sponsor in the best interests of the participants. Therefore, if deemed necessary, the Investigator can implement an immediate change to the protocol for safety reasons with notification to the medical monitor as soon as practicably possible. This means that, exceptionally, the implementation of urgent amendments will occur before submission to, and approval by, the HREC(s). In such cases, the Principal Investigator must notify the Sponsor within 24 hours. A related substantial amendment will be written and submitted to HREC(s) as soon as practicable but no later than 7 working days, together with a description of the steps that have already been taken in regard to implementation of this amendment.

HREC approval of future research

In the event that the Principal Investigator or the Sponsor want to perform testing on the samples that is not described in the protocol, additional approval will be sought from the approving HREC(s).

